Management of psychosocial stress is an important aspect in post-stroke management. Prolonged psychosocial stress is an established risk factor of mortality and stroke-related complications [13]. Depression and psychosocial stress are risk factors for stroke; while stroke is known to be a strong risk factor for depression and stress [29]. Cortisol is a stress biomarker and an objective measure of psychological stress that reflects the hypothalamic-pituitary-adrenal (HPA) axis functioning. A previous study has showed that elevated cortisol is correlated with increased stroke severity; and such distortion in diurnal cortisol profile is linked with longer hospital stay for inpatients, higher dependency, greater risk of depression and delirium for outpatient stroke survivors [30]. Given the important implication of psychological distress and cortisol on stroke severity and rehabilitation outcome, it is important to examine the changes in psychological distress as well as cortisol profiles during the rehabilitation period.

The need for a holistic, arts-based approach to stroke rehabilitation

With the increasing post-stroke survival rates and a younger age of onset, reduction of morbidity and achieving a better quality of life after stroke becomes a more pressing aim during survivorship [7]. Along with regaining the ability to perform daily activities properly, literature highlights the importance of reestablishing connection with others and the ability to affirm life though a rehabilitation with the deity, self, community, and environment that nurtures wholeness, which in turn improves compliance to rehabilitation and recovery outcomes [31].

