Nevertheless, systematic study related to arts-based intervention has not yet been conducted, in particular for younger stroke survivors, who may face bigger and longer-term impacts in the psychophysiological and social-spiritual outcomes. The present study primarily examines the effectiveness of an Expressive Arts-based Intervention on bio-psychosocial-spiritual outcomes in younger Chinese stroke survivors as compared with the treatment-as-usual control group across different time points. It also aims to explore the associations between the psycho-social-spiritual variables and cortisol profiles as well as the changes of such association across time. Besides, this study also targets at understanding younger stroke survivors' first person body perception and the body-mind mechanism among them. Moreover, participants' nature of ischemic or hemorrhagic stroke will be accounted for using statistical methods to explore common and differential effects of Expressive Arts-based Intervention on both types of stroke.

Study Aims

Primary objectives:

To investigate the short and longer-term effects of an Expressive Arts-based Intervention on younger and pre-elderly Chinese stroke survivors on:

- (a) Depressive and anxiety symptoms
- (b) Perceived stress
- (c) Perceived social support
- (d) Self-esteem
- (e) Hope
- (f) Subjective and spiritual well-being
- (g) Stroke-related and general related quality of life
- (h) Salivary cortisol level

Secondary objectives:

- (a) To examine the associations between cortisol levels, diurnal cortisol profiles and psychosocial-spiritual variables in participants
- (b) To examine the changes of the associations between cortisol levels, diurnal cortisol profiles and psycho-social-spiritual variables across the time points.

Study hypotheses

- 1. Expressive Arts-based Intervention is more effective than treatment-as-usual control in
 - (a) reducing depressive and anxiety symptoms
 - (b) reducing stress
 - (c) enhancing perceived social support
 - (d) enhancing self-esteem
 - (e) fostering hope
 - (f) cultivating subjective and spiritual well-being
 - (g) enhancing stroke-related and general quality of life
- 2. Expressive Arts-based Intervention group will be different from control group in altering salivary cortisol levels and profiles
- 3. The associations between cortisol profiles and psychosocial-spiritual variables and the changes of such associations across the time points are exploratory in this study.

Methodology

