The Treatment-As-Usual Control group will continue with routine healthcare and rehabilitation services. They would be given the option to participate in the Expressive Arts-based Intervention after the 8-month study period.

Ethical consideration

The study is reviewed by the Human Research Ethics Committee (HREC) and the Institutional Review Board of the University of Hong Kong/Hospital Authority Hong Kong West Cluster (HKU/HA HKW IRB). Written informed consent will be obtained from the participants before screening, assessment and randomization. To ensure confidentiality, participant codes will be assigned to represent the participants. All data collected will be stored in locked storage and destroyed 3 years upon study completion.

Outcome measurements

Assessments pertain to areas of psycho-social-spiritual well-being of stroke survivors, including (a) emotional distress, (b) psychosocial functioning, (c) quality of life, (d) physiological biomarkers, and (e) demographics and clinical details. Self-related questionnaires and salivary cortisol are administered by the participants while blood pressure, heart rate, will be measured by a trained research assistant blinded to the randomization. All measurements are taken at all study time points except for demographics and clinical details. Since the impairment levels of stroke survivors vary and may affect rehabilitation progress and intervention outcomes, a disability assessment will be used as a screening tool to understand the physical condition of the participants and for recruitment of the participants into the trial.

Screening

Disability. The Modified Rankin Scale is a clinician-reported rating scale for measuring the degree of disability of the stroke participants. The scale is rated on an ordinal scale of 0 to 6, with a higher score denoting higher level of disability post-stroke [47].

Outcome measures

Emotional distress

Depression and anxiety. The Chinese version of the Hospital Anxiety and Depression Scale [48] captures anxiety and depressive symptoms. The 14-item, 4-point scale measures anxiety (7-item) and depression (7-item) subscales. The measure will be used as an outcome measure on mental health distress.

Perceived stress. Perceived stress will be assessed by the Chinese Perceived Stress Scale [49]. Using a 5-point Likert scale (0-4), the scale consists of 10 items about the degree to which life events are appraised as stressful.

Psychosocial functioning

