Salivary Cortisol. Saliva samples will be collected by the participants at five prescribed time points (awakening, 45-minute post-awakening, 12 noon, 5pm, and 9pm) on two consecutive days using the collection device package, Salivette, which includes a cotton swab to place under the tongue. A trained research assistant with prior experience in using the Salivette kit will explain the collection procedures to the participants in details. A record sheet will also be included in the package to document the participants' health behaviors and activities on the day of saliva collection that might affect the diurnal cortisol rhythm, including (a) smoking habit, (b) consumption of alcohol/coffee drinking on that day, and (c) subjective evaluation of sleep quality, total sleep duration, stress levels on a scale of 1 to 10. All of these measures may affect the diurnal cortisol rhythm and will be controlled in the analysis.

Demographics and clinical details

Demographics. Socio-demographic, such as age, gender, education level, employment and financial status, and marital status will be documented based on self-report questionnaires.

[figure not shown]
Clinical data. Participants' clinical profile including the type of stroke, time lapse from first occurrence, onset and history of psychiatric disturbance, presence of comorbidity if any (such as physical disabilities, hypertension, diabetes mellitus, or any other form of vascular disease), treatment and medication record, and psychosocial support and/ or rehabilitation service utilization will be documented.

Data analyses

Effectiveness of Expressive Arts-based Intervention group: Analysis of variance and chi-square independence tests will be carried out using SPSS to compare the demographic profile of the two groups. Latent growth modeling in Mplus will be used to explore the effectiveness of the intervention over the assessment points in comparison with the control group. All variables including the demographic variables (e.g. age, gender, education etc.) will be accounted for in the analysis.

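### Cortisol is to be controlled for the same-day stress rating; applied to the between-arm comparison, this adjusts for a post-randomisation variable, and the contrast may no longer estimate the total effect

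*Combined protocol and SAP*

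**What the plan says.** The Salivary Cortisol paragraph (Psychophysiological biomarkers) describes a record sheet supplied in the saliva package. It covers smoking, alcohol or coffee that day, and "subjective evaluation of sleep quality, total sleep duration, stress levels on a scale of 1 to 10". The rule for these items is: "All of these measures may affect the diurnal cortisol rhythm and will be controlled in the analysis". No model and no visit is named.

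Outcome measurements states: "All measurements are taken at all study time points except for demographics and clinical details". Since the sheet comes with the saliva kit, this implies stress ratings at T0, T1 (week 8) and T2 (six months after the intervention).

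Under Data analyses, effectiveness against control is assigned to latent growth modelling. That paragraph also says that all variables will be taken into account, giving only age, gender and education as examples. The paragraph on salivary cortisol lists three indices (daily mean, area under the curve, diurnal slope) and a two-level growth curve model for the five daily samples within participants. It gives no arm term, visit structure or covariate list.

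Salivary cortisol is primary objective (h). Hypothesis 2 reads: "Expressive Arts-based Intervention group will be different from control group in altering salivary cortisol levels and profiles". Hypothesis 1 includes "b) reducing stress". The background section says: "Cortisol is a stress biomarker and an objective measure of psychological stress". The first secondary objective is: "To examine the associations between cortisol levels, diurnal cortisol profiles and psychosocial-spiritual variables in participants".

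**The concern.** Randomisation protects a comparison of arms that is unadjusted or adjusted for baseline variables. It does not protect one adjusted for something measured after allocation that the intervention may alter. The T1 and T2 stress ratings are of that kind: the trial expects the intervention to reduce stress and treats cortisol as a marker of stress, so on its own reasoning the rating may lie between arm and cortisol.

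If the rating enters the H2 model, any effect that runs through it is removed from the contrast. What remains is not a clean direct effect either if stress and cortisol share unmeasured causes. The estimate could be attenuated (the stress path and the total effect share a sign), inflated (opposite signs), or non-zero with no true effect (shared causes only). H2 is non-directional and the documents do not settle which applies.

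Two analysts could also both follow the text, one including the T1/T2 rating in H2 and the other not, and reach different answers on a primary objective.

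**Working it through.** The plan gives no figure on this point to reproduce. It states neither an arm effect on the same-day rating nor a stress-cortisol slope.

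**Step 1: which text governs H2.**
- The record-sheet rule covers every item and names no model or visit.
- The effectiveness paragraph is open-ended on covariates, though its only examples are baseline demographics.
- The two-level model has no covariate list.
- Nothing separates the covariates for H2 from those for the association objectives. The adverse reading is therefore permitted, not required.

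**Step 2: size of the shift.** Set the within-arm SDs of the rating and of cortisol to 1. Let a be the arm effect on the T1/T2 rating and b the within-arm slope of cortisol on the rating. In a linear model:

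adjusted contrast = total effect − a × b.

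Assumed inputs: a = 0, 0.15, 0.30, 0.63; b = 0.1, 0.2, 0.3, 0.5. The largest a borrows the planning d of 0.63 from the sample-size section, which is not assigned to any outcome. Absolute shifts in SD:

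| a | b = 0.1 | b = 0.2 | b = 0.3 | b = 0.5 |
|---|---|---|---|---|
| 0 | 0 | 0 | 0 | 0 |
| 0.15 | 0.015 | 0.030 | 0.045 | 0.075 |
| 0.30 | 0.030 | 0.060 | 0.090 | 0.150 |
| 0.63 | 0.063 | 0.126 | 0.189 | 0.315 |

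Example: with an assumed total effect of 0.63, the same sign throughout, a = 0.63 and b = 0.3, the adjusted contrast is 0.63 − 0.189 = 0.441.

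**Step 3: checks by simulation.**
- 58 per arm, 4,000 trials per cell, total effect 0.63, a = 0.63: adjusted contrast 0.567 / 0.503 / 0.444 for b = 0.1 / 0.2 / 0.3. Unadjusted: 0.62 to 0.64 in every cell.
- No true effect, association due only to shared causes, a = 0.63: adjusted contrast 0.062 / 0.130 / 0.190. Unadjusted: within 0.006 of zero in every cell.
- One large sample of 400,000, a and total effect both −0.63, b = 0.1 / 0.2 / 0.3 / 0.5: adjusting for the T1 rating gives −0.565 / −0.506 / −0.437 / −0.314. Adjusting for the T0 rating only gives −0.629 / −0.632 / −0.625 / −0.625, the same as no adjustment.
- The same large-sample setting plus an unmeasured common cause loading 0.3 on both variables: T1-adjusted contrast −0.51 / −0.45 / −0.39 for b = 0.1 / 0.2 / 0.3.

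**Step 4: cost of leaving the rating out.** The standard-error ratio, adjusted to unadjusted, is √(1 − b²) × √(1 + a²/4). The cost of omission is 1/ratio − 1:

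| a | b = 0.1 | b = 0.2 | b = 0.3 | b = 0.5 |
|---|---|---|---|---|
| 0 | +0.5% | +2.1% | +4.8% | +15.5% |
| 0.63 | −4.1% | −2.6% | 0.0% | +10.1% |

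For example, at a = 0 and b = 0.5: 1/√0.75 − 1 = 15.5%.

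All of this concerns a single comparison of two means. The planned latent growth model cannot be rebuilt from the document, so no power or false-positive figure is given.

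**The case against.** The strongest reply is that the plan may never intend this adjustment for H2. The rule is justified by influence on the diurnal rhythm, and the model closest to that rhythm is the two-level model. Its stated purpose is exploratory and concerns relationships among variables, which fits the secondary objectives. Controlling for same-day state is reasonable there, and no arm contrast is biased. This stands as a plausible reading. It does not settle the matter, because that model is also meant to describe change in cortisol over time and could serve H2, and because the rule itself has no limit.

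A second reply is that adjustment alone does not move the estimate. That is correct: if the arm does not change the rating, or the rating is unrelated to cortisol within arm, the shift is zero.

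A third is that the rating is not the hypothesis 1(b) instrument: "Perceived stress will be assessed by the Chinese Perceived Stress Scale". Also correct. The point needs only that the daily rating is close to that target, not that it is the same measure.

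A reader might go further and infer that same-day smoking, alcohol or coffee, and sleep are wrongly controlled too. They are also recorded after randomisation, but none is a stated target of the intervention. Adjusting for them is a trade-off and is not treated as an error here.

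**Conclusion.** The point holds in conditional form and should be fixed. As written, the rule reaches the between-arm cortisol comparison and would condition it on a post-randomisation stress rating. The contrast may then no longer estimate the total effect. Four conditions are needed: the rule is applied to the H2 model; T1/T2 values are used; the intervention changes the rating; and the rating is related to cortisol within arm. The first two follow from a literal reading of the plan, and the last two are not established by the documents.

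A reader might infer that the H2 result will be biased, or biased towards no difference. The documents support neither: they do not show that this model is intended for H2, and they fix neither the sign nor the size of a × b. Nor is 0.19 or 0.32 SD a limit; each is the edge of a chosen grid. The three cortisol indices need not share one slope on stress, so the shift could differ between them.

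**What to change.** Amend the Salivary Cortisol paragraph and Data analyses, in about three sentences:

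- The between-arm cortisol comparisons (H2, each index) do not adjust for the T1 or T2 stress rating; the T0 rating may be used.
- The T1/T2 ratings are kept for the association analyses (secondary objectives, hypothesis 3) or for a mediation or sensitivity analysis labelled as such.
- State which of these purposes the two-level model serves.

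No change is required for smoking, alcohol or coffee, or sleep. No new data are needed and the sample size is unaffected. The downside is some loss of precision: under the assumed inputs, about 5% or less in standard error for a within-arm slope up to 0.3, and about 10 to 15% at a slope of 0.5.

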Analysis of Salivary Cortisol Data: Saliva sample will be centrifuged at 3,000 rpm for 10 minutes at room temperature. Cortisol level will be determined with an enzyme-linked immunoabsortbent assay kit (EIA, Salimetrics, Inc). The assay sensitivity is 0.193 nmol/l and the intra-assay and inter-assay coefficients of variation are 3% and 10% respectively. The mean cortisol level across the day, total cortisol level indexed by the area under the curve, and the diurnal cortisol slope will be calculated. To explore individual trajectories of changes in cortisol level over time and the complex relationships between different variables, a two-level individual growth curve model using Mplus software will be adopted since cortisol measures at 5 daily time points are nested within participants. The method is an appropriate variant of multiple regression modeling for the nested structure of cortisol data.

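### The cortisol growth model is justified by 5 daily samples within participants, but the samples lie in 2 days within 3 assessments, and the plan does not say how those groupings enter or which analysis tests hypothesis 2

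*Combined protocol and SAP*

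**What the plan says.** Under Data analyses, the paragraph on salivary cortisol adopts "a two-level individual growth curve model using Mplus software will be adopted since cortisol measures at 5 daily time points are nested within participants". It adds: "The method is an appropriate variant of multiple regression modeling for the nested structure of cortisol data". The purpose given is "To explore individual trajectories of changes in cortisol level over time", together with relationships between variables. The same paragraph derives three indices: a daily mean, an area under the curve (AUC) and a slope ("the diurnal cortisol slope will be calculated"). It contains no arm term and no arm-by-assessment term.

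The data structure is set in other sections:

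- Psychophysiological biomarkers, Salivary Cortisol: five samples a day, on two consecutive days.
- Research design: three assessments (T0, T1 at week 8, T2 six months after the intervention).
- Outcome measurements: everything except demographics and clinical details is measured at each assessment.

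Cortisol is primary objective (h), under the aim "To investigate the short and longer-term effects of an Expressive Arts-based Intervention". Hypothesis 2 reads: "Expressive Arts-based Intervention group will be different from control group in altering salivary cortisol levels and profiles". The effectiveness paragraph of Data analyses says "Latent growth modeling in Mplus will be used to explore the effectiveness of the intervention over the assessment points", compared with control, but lists no outcomes. Secondary objective (b) is "To examine the changes of the associations between cortisol levels, diurnal cortisol profiles and psycho-social-spiritual variables across the time points".

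**The concern.** The only nesting that the cortisol paragraph recognises is daily samples within participants, and it presents the model as adequate on that basis. The two middle groupings, day and assessment, are left out. Samples from the same assessment or the same day share whatever was particular to that person at that time. A model with only a participant effect treats them as independent given the person, and so counts ten samples at an assessment as ten independent pieces of information about that assessment.

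Hypothesis 2 is about change between assessments, which is where this matters. The plan has two candidate models and three indices, and assigns none of them to hypothesis 2. An analyst could choose, after seeing the data, between fits whose standard errors differ. If the pooled fit were chosen, the test of change in cortisol level would risk false positives on a primary objective.

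**Working it through.** **Count.** The plan gives no sample size or variance figure for cortisol, so the structure is what can be checked: 5 samples x 2 days x 3 assessments = 30 per participant, against the 5 within participants named in the model.

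**Variance of a change in level.** Set within-person variance to 1 = v + d + e, where v is the assessment share, d the day share and e the residual. An assessment mean over 10 samples has within-person variance v + d/2 + e/10. A pooled model with a participant intercept takes it to be about 1/10. The ratio of true to assumed variance for T1-T0 change is therefore

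R = 10v + 5d + e,

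and the standard error is too small by a factor of √R. Because R - 1 = 9v + 4d, it is too small whenever v or d exceeds zero. For v = d = 0.05, R = 0.50 + 0.25 + 0.90 = 1.65 and √1.65 = 1.28. The nominal 5% test then rejects when |z| > 1.96/1.28 = 1.53, which happens about 13% of the time. A participant random slope over time of day does not alter this, because it cancels from a difference between assessments sampled at the same prescribed times.

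**Range.** All shares are assumptions. The simulation has 58 per arm (half of the plan's 116), no true effect, no missing data, waking assumed at 07:00, and 6,000 runs per row. Only levels vary. The last three columns are type I error for T1-T0.

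| Assessment + day share | R | SE factor | Level, pooled | Level, per-assessment summaries | Diurnal slope, pooled |
|---|---|---|---|---|---|
| 0% + 0% | 1.00 | 1.00 | 5.1% | 5.1% | 5.1% |
| 2% + 2% | 1.26 | 1.12 | 8.2% | 4.8% | 5.1% |
| 5% + 5% | 1.65 | 1.28 | 12.6% | 4.8% | 4.0% |
| 10% + 5% | 2.10 | 1.45 | 17.8% | 4.9% | 3.7% |
| 20% + 10% | 3.20 | 1.79 | 29.8% | 5.8% | 2.4% |

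Participant-clustered standard errors gave 5.2% to 6.2% for the level test over the same rows.

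**Diurnal slope.** Let vs and ds be the shares for slopes that vary by assessment and by day, so that v + d + vs + ds + e = 1. The ratio for change in slope is 10vs + 5ds + e. If only levels vary it equals e, which is below 1, and the test is conservative. The standard error is too small only if 9vs + 4ds > v + d. With v = d = vs = ds = 0.05, e = 0.80, the ratio is 0.50 + 0.25 + 0.80 = 1.55 and the simulated error is 12.3%.

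**Participant random slope over assessment time.** Take T2 as week 8 + 26 = 34. The weeks 0, 8, 34 have mean 14 and sum of squares 196 + 36 + 400 = 632. Of the 2 variance units in T1-T0, the linear trend carries 8²/632 = 64/632 = 0.10. The ratio becomes 2R/(0.10R + 1.90). At R = 1.65 this is 3.30/2.065 = 1.60, and the simulated error is 12.4%, so T1-T0 is hardly protected. A linear-time test under the same model is protected (4.5% to 5.7% over the five rows).

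**Participant-level effects for each assessment.** In one simulated data set with shares 10% + 5%, the standard error of arm by T1 was 0.081 with a participant intercept only, 0.107 with a participant-level effect for each assessment, and 0.107 from per-assessment summaries. A model that is still two-level in name can therefore be right for this contrast.

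**The case against.** The strongest reply is that the plan already has a place for hypothesis 2. The effectiveness paragraph assigns the arm comparison over assessments to latent growth modeling, the trial is sized on that model, and the per-assessment mean, AUC and slope are natural inputs to it. The two-level sentence mentions neither arm nor control, and its purpose fits the exploratory associations. On this reading the problem does not arise.

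Further, the harm needs several unstated choices together: all samples pooled, no participant-level assessment effects, model-based standard errors and a T1-T0 contrast. No section specifies that contrast; the short-term effect is an aim, not a named test. The plan also promises to control for smoking, alcohol or coffee, sleep and stress on the collection day, which could absorb part of the day and assessment variance.

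Much of this stands, and it rules out two stronger readings. A reader might infer that two levels are wrong in themselves; they are not, since participant-level assessment effects or participant-clustered robust standard errors make such a model valid. A reader might also infer that the plan commits to an invalid test of hypothesis 2; the text does not commit to any test of it.

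The reply does not close the gap. The effectiveness paragraph names neither cortisol nor an index, the cortisol paragraph gives cortisol its own model, and both are introduced as exploring something, so that wording does not separate them. No estimator or standard-error method is stated.

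**Conclusion.** The point stands as a conditional risk on a primary objective. Two things follow from the documents alone: the stated justification omits the day and assessment groupings, and no index, contrast or model is assigned to hypothesis 2.

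For the literal pooled fit with model-based standard errors, the direction of the error for change in level is also established: the standard error is too small whenever levels vary between a person's assessments or days. Its size is not known for this trial. About 13% type I error at assumed shares of 5% + 5% is an illustration, and the range tried runs from 5% (no such variance) to about 30%. For the diurnal slope, the profiles part of hypothesis 2, the test may be conservative or anti-conservative depending on whether slopes themselves vary.

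It would go too far to say that the cortisol results will carry inflated error. That depends on choices the plan leaves open, and several natural choices avoid it.

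**What to change.** In the salivary cortisol paragraph of Data analyses:

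1. State that hypothesis 2 is tested with per-assessment cortisol summaries, averaged over the two days, in the latent growth model of the effectiveness paragraph.
2. Name one lead index for level and one for profile.
3. Name the arm-by-time contrast and the time coding. If the short-term effect is to be tested, use non-linear time or separate T1 and T2 contrasts, because a linear trend does not test T1-T0 on its own.
4. Limit the two-level model to the within-day curve and the exploratory associations. Wherever it compares assessments, including secondary objective (b), add random effects for assessment and day (on the diurnal slope too where profiles are compared) or participant-level assessment effects, or specify participant-clustered robust standard errors.

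The cost is a few sentences and no new data, since the summaries and the latent growth model are already planned. Standard errors for level change will be larger than in the pooled fit. The record-sheet covariates must also be averaged over the two days, and a rule is needed for missing samples when AUC and slope are computed.
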